**Figure KHAA.6.1. Graphical testing scheme for Study KHAA.**

## 6.7. Patient Disposition

An overview of patient populations will be summarized by treatment group. Frequency counts and percentages of patients excluded prior to randomization by primary reason for exclusion will be provided for patients who failed to meet study entry requirements during screening.

Patient disposition will be summarized using the ITT population. Frequency counts and percentages of patients will be summarized by treatment group by the following dispositions:

- dosing (study drug) period disposition:
  - ongoing dosing (study drug) period
  - discontinued dosing (study drug) period
  - completed dosing (study drug) period
- treatment period disposition:
  - ongoing treatment period
  - discontinued treatment period (reason will be summarized)
  - completed treatment period
- study disposition:
  - ongoing
  - discontinued (reason will be summarized)
  - completed

A listing of patient disposition will be provided for all randomized patients, with treatment assignment, the extent of their participation in the study, and the reason for discontinuation.

## 6.8. Patient Characteristics

### 6.8.1. Demographics

Patient demographics will be summarized as described above. The following demographic information will be included:

- age
- age group (<65 vs. ≥65)
- age group (<65, ≥65 to <75, ≥75 to <85, ≥85)
- gender (male, female)
- race (American Indian or Alaska Native, Asian, Black or African American, Native Hawaiian or Other Pacific Islander, White, Multiple)
- geographic region (US, Europe, Rest of World)
- country

- weight (kg)
- weight category (<60 kg, ≥60 to <100 kg, ≥100 kg)
- height (cm)
- body mass index (BMI) (kg/m^2)
- body mass index category (<25 kg/m^2, ≥25 to <30 kg/m^2, ≥30 kg/m^2), and
- baseline renal function status: impaired (estimated glomerular filtration rate [eGFR] <60 mL/min/1.73 m^2) or not impaired (eGFR ≥60 mL/min/1.73 m^2).

A listing of patient demographics will also be provided for the ITT population.

### **6.8.2. Baseline Disease Characteristics**

The below baseline disease information (although not inclusive) will be categorized and presented for baseline coronavirus disease 2019 (COVID-19) clinical characteristics, baseline health outcome measures, and other baseline demographic and disease characteristics as described above:

- duration of symptoms prior to enrollment (≥7 days or <7 days)
- World Health Organization (WHO) ordinal scale
- baseline disease severity:
  - hospitalized not requiring supplemental oxygen, requiring ongoing medical care
  - hospitalized requiring supplemental oxygen by prongs or mask
  - hospitalized requiring noninvasive ventilation or high-flow oxygen
- inflammatory biomarkers:
  - C-reactive protein, high-sensitivity (hs-CRP)
  - Ferritin
  - D-Dimer
  - Lactate dehydrogenase (LDH)
- Prior therapy of interest: nonsteroidal anti-inflammatory drugs (NSAIDs), Antivirals, Antibiotics, Immunosuppressants (anti-malarials, corticosteroids and others)
- Symptom onset (<7 days, ≥7 days)
- Disease duration of symptoms prior to enrollment (<7 days, ≥7 days)
- Renal function status (impaired, no impaired)
- Preexisting comorbid conditions (None, Any; obesity; diabetes, chronic respiratory disease, hypertension)

- dexamethasone and/or other systemic corticosteroid used at baseline for primary study condition (Yes/No)
- remdesivir (Yes/No)

### **6.8.3. Historical Illness and Preexisting Conditions**

Historical illnesses are defined as those conditions recorded in the Preexisting Conditions and Medical History electronic case report form (eCRF) or from the Prespecified Medical History: Comorbidities eCRF with an end date prior to the informed consent date. The number and percentage of patients with selected historical diagnoses will be summarized by treatment group using the ITT population. Historical diagnoses will be categorized using the Medical Dictionary for Regulatory Activities (MedDRA; most current available version) algorithmic Standardized MedDRA Queries (SMQs) or similar pre-defined lists of Preferred Terms (PTs) of interest.

Preexisting conditions are defined as those conditions recorded in the Pre-existing Conditions and Medical History eCRF, or the Prespecified Medical History: Comorbidities eCRF with a start date and time prior to the informed consent and with a stop date that is after the informed consent date or have no stop date (ongoing). Adverse events (AEs) are recorded in the eCRFs. For events recorded on the AE page, we considered it as a preexisting event if its onset date was before the first dose date. For events occurring on the day of the first dose of study treatment, the date and time of the onset of the event will both be used to determine if the event was preexisting. Conditions with a partial or missing start date (or time if needed) will be assumed to be 'not preexisting' unless there is evidence, through comparison of partial dates, to suggest otherwise. Preexisting conditions will be categorized using the SMQs or similar predefined lists of PTs of interest. Frequency counts and percentages of patients with selected preexisting conditions will be summarized by treatment group using the ITT population.

The number and percentage of participants using preferred terms of prior medications will be presented.

The following historical illness and preexisting conditions will be presented:

- preexisting comorbid conditions:
  - none, any
- preexisting comorbid conditions of interest
  - obesity
  - diabetes (Type I and Type II)
  - chronic respiratory disease
  - hypertension

### **6.9. Treatment Compliance**

As all study drug doses will be administered at the study site, treatment compliance will not be reported.

## 6.10. Concomitant Therapy

Medications will be classified into anatomical therapeutic chemical (ATC) drug classes using the latest version of the WHO drug dictionary. Medication start and stop dates will be compared to the date informed consent is obtained to allow medications to be classified as concomitant.

*Prior medications* are those medications that start and stop prior to the date of the first dose of study treatment. *Concomitant medications* are those medications that start before, on, or after the first day of study treatment and continue into the treatment period. For all summary tables of concomitant medications, PTs of concomitant medication will be sorted by descending frequency in the LY total arm.

If dose-related corticosteroid analyses are conducted, the information in [Appendix 1](#) will be used as reference for a conversion factors for each corticosteroid medication identified during the study, instructions for selecting corticosteroids, and the manual review process.

**Table KHAA.6.3. Summary Tables Related to Concomitant Medications**

Analysis	Details
Prior medications	Number and percentage of participants using Preferred Terms of prior medication 
 
Ordered by decreasing frequency
 
 No inferential statistics
Concomitant medications	Number and percentage of participants using Preferred Terms of concomitant medication 
 
Ordered by decreasing frequency
 
 No inferential statistics

## 6.11. Efficacy Analyses

The general methods used to summarize efficacy data, including the definition of baseline value for assessments are described in [Section 6.1](#).

[Table KHAA.6.4](#) includes the descriptions and derivations of the primary, key secondary, and associated supportive analysis efficacy outcomes.

[Table KHAA.6.5](#) provides the detailed analyses including analysis type, method and imputation, population, time point, and comparisons for efficacy analyses.

[Table KHAA.6.6](#) includes the descriptions and derivations of the other secondary and associated supportive analysis efficacy outcomes.

[Table KHAA.6.7](#) provides the detailed analyses including analysis type, method and imputation, population, time point, and comparisons for efficacy analyses.

### 6.11.1. Primary Outcome and Methodology

The primary comparison of interest is the proportion of patients who die or require non-invasive ventilation/high-flow oxygen or invasive mechanical ventilation (including ECMO) by Day 28. The primary comparison will be performed on two different populations:

- Population 1 – all randomized patients
- Population 2 – patients who, at baseline, require oxygen supplementation and are not receiving dexamethasone or other systemic corticosteroids for the primary study condition.

Patients on non-invasive ventilation/high-flow oxygen at baseline will be counted toward this endpoint if they progressed to invasive mechanical ventilation. Treatment comparisons between baricitinib 4-mg QD + background therapy and placebo + background therapy will be made using logistic regression with baseline stratification factors and treatment group in the model.

- Pr.V: Proportion of patients who died or require non-invasive ventilation/high-flow oxygen or invasive mechanical ventilation (including ECMO) by Day 28. For patients who start with ventilation at baseline, the patients need to be worsening in symptom (at least 1-point worsening in NIAID-OS) to be counted.

For the primary comparison involving two different populations, the alpha will be split between the two populations such that 99% of alpha is assigned to Population 1 and the rest to Population 2. The primary endpoint will be met if any one or both of these two populations show a significant treatment effect.

If the sample size is increased as a result of the interim analysis, the Cui, Hung, and Wang (CHW) procedure (Cui et al. 1999) will be applied to the primary endpoints for the two populations and the secondary endpoints to control the type I error at a one-sided  $\alpha=0.025$  significance level. The CHW method ensures strong control of type I error when the sample size is increased in a data dependent manner. Details about the CHW statistics are provided in Section 6.16.2.4.

If the sample size is increased as a result of the interim analysis, an unadjusted point estimate for both of the primary efficacy analysis will be calculated and reported. A median unbiased point estimate and a stage-wise adjusted confidence interval for the primary efficacy analysis will be calculated and reported based on the approach described by Brannath and colleagues (Brannath et al. 2009) to assess sensitivity of the point estimate.

No CHW adjustments will be applied to the endpoints if the recommended increased number of patients from the sample size re-estimation had already been enrolled before the completion of the interim.

Table KHAA.6.4 and Table KHAA.6.6 include the descriptions and derivations of the primary and secondary outcomes.

Table KHAA.6.5 and Table KHAA.6.7 provide the detailed analyses including analysis type, method and imputation, population, time point, and comparisons for efficacy analyses.

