#### Testing Scheme for the Primary Analyses

The 1-sided p-values and associated test statistics are defined as

- p1 is the 1-sided p-value for Population 1; z1 is the associated test statistic
- p2 is the 1-sided p-value for Population 2; z2 is the associated test statistic

The hypotheses are

- H01 is the null hypothesis corresponding to Population 1
- H02 is the null hypothesis corresponding to Population 2

H01 will be rejected if:

•  $p_1 < \alpha_1 \text{ OR } (p_1 < 0.025 \text{ AND } p_2 < \alpha_2)$ 

H02 will be rejected if:

•  $p_2 < \alpha_2 \text{ OR } (p_2 < 0.025 \text{ AND } p_1 < \alpha_1)$ 

 $\alpha_1$  and  $\alpha_2$  are critical thresholds preserving the overall 1-sided type 1 study error at 0.025.

If either of the two tests is significant, then the study will be declared successful.

The testing scheme will provide a strong control of Type-I error for the study at a 1-sided 0.025 level and is based on the closed testing principle (Marcus et al. 1976). The testing scheme is parametric, where the known correlation is accounted for between the 2 test statistics  $z_1$  and  $z_2$ .

The  $\alpha_1$  for Population 1 will be pre-specified in the Statistical Analysis Plan (SAP). The  $\alpha_2$  for Population 2 will be calculated to control the study Type I error rate at 0.025, accounting for the prespecified value of  $\alpha_1$  and the correlation between the two test statistics. If the Population 1 test is rejected and the Population 2 test is not, or vice versa, the remaining  $\alpha$  will be recycled and used for subsequent testing of the population that was not significant (Millen and Dmitrienko 2011). The final  $\alpha$  levels will be based on the percentage of Population 2 within Population 1 observed in the final analysis data set. Additional details will be described in the SAP.

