## 6.6. Multiple Comparisons/Multiplicity

Multiplicity controlled analyses will be performed on the primary and key secondary endpoints to control the overall family-wise Type I error rate at a 1-sided  $\alpha$  level of 0.025. The graphical multiple testing procedure described in Bretz et al. (2011) will be used. The graphical approach is a closed testing procedure; hence it strongly controls the family-wise error rate (FWER) across all endpoints (Alosh et al. 2014).

[figure not shown]
See [Figure KHAA.6.1](#) for the graphical testing scheme for this study. This scheme allows for some  $\alpha$  to be sent to the key secondary analyses if Population 1 achieves statistical significance (see next paragraph). Note that for the 2 primary populations the scheme is slightly different from what is in the protocol. As the testing scheme only impacts interpretation of the results and not the actual analysis, there is no plan to update the protocol.

If Population 2 is rejected at  $\alpha_2$ , Population 1 will be tested at level  $\alpha$ , otherwise Population 1 will be tested at level  $\alpha_1$ . If Population 1 is rejected, each of the gated secondaries will be tested in order until one is not rejected as depicted in [Figure KHAA.6.1](#). The key secondaries will be tested at level  $\alpha_1$  if Population 1 was rejected or at level  $\alpha$  if both Population 1 and Population 2 were rejected. Finally, if Population 1 and all secondaries are rejected at level  $\alpha_1$ , but Population 2 was not rejected at level  $\alpha_2$ , Population 2 will be tested again at level  $\alpha$ .

The testing scheme will provide a strong control of Type-I error for the study at a 1-sided 0.025 level and is based on the closed testing principle (Marcus et al. 1976). The testing scheme is parametric, where the known correlation is accounted for between the 2 test statistics  $z_1$  and  $z_2$ . The initial significance levels for the Primary endpoints Population 1 ( $\alpha_1$ ) and Population 2 ( $\alpha_2$ ) will be computed using the fact that their test statistics have a correlation of  $\sqrt{p}$  where  $p$  is the percentage of Population 2 within Population 1 observed in the final analysis data set and a 0.99 weight on Population 1 and 0.01 weight on Population 2. The two significance levels will be computed using the R package gMCP.

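### The starting significance levels of the two primary tests are written inconsistently, and SAP 6.6 passes a correlation-scaled level to the key secondaries, so strong control at 0.025 is not exact there (minor)

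*SAP*

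**What the plan says.** Three current passages set the first-step levels, called alpha1 (Population 1, all randomized) and alpha2 (Population 2, on oxygen without systemic corticosteroids). The overall level is one-sided 0.025.

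- **SAP 6.11.1** states a split: "99% of alpha is assigned to Population 1 and the rest to Population 2". It does not mention correlation.
- **SAP 6.6** takes sqrt(p) as the correlation of the two statistics. Here p "is the percentage of Population 2 within Population 1 observed in the final analysis data set". The weights are 0.99 for Population 1 and 0.01 for Population 2. It adds: "The two significance levels will be computed using the R package gMCP". It also says that the scheme for the two primaries departs a little from the protocol, that the protocol will not be updated, and that the graphical scheme is final.
- **Protocol 9.1** leaves alpha1 to be fixed in advance in the SAP. The second level, by contrast, is solved: the threshold "for Population 2 will be calculated to control the study Type I error rate at 0.025, accounting for the prespecified value of" the first one. The calculation also takes in how strongly the two statistics correlate.

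The trial succeeds if either primary is significant (Protocol 9.1 and 9.4.2, SAP 6.11.1). Under SAP 6.6 the key secondaries are tested at alpha1 if only Population 1 is rejected and at the full alpha if both are. SAP 6.6 claims strong family-wise control at one-sided 0.025 over the primary and key secondary endpoints.

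**The concern.** A primary threshold should have one value that can be computed without choosing between passages. Here a reader can compute alpha1 in two ways and alpha2 in two ways.

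- If Population 1 misses and the Population 2 p-value lies between about 0.00025 and the protocol's alpha2, the protocol declares success and both SAP sections declare failure.
- If Population 2 misses and the Population 1 p-value lies between 0.02475 and about 0.0248 to 0.0249, the two SAP sections disagree. The gate to every key secondary turns on that answer.

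The second issue concerns error control. Correlation scaling lets alpha1 + alpha2 exceed 0.025 because the correlation of the two primary statistics is known. A key secondary that inherits the scaled alpha1 does not have that known correlation with the Population 2 statistic.

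**Working it through.** **Inputs.** One-sided 0.025, the 0.99/0.01 weights and correlation sqrt(p) are from SAP 6.6. N = 1400 is from Protocol 9.2 and SAP 5.2. The 25% placebo rate is from Amendment D in Protocol 9.2; no rate is restated for Amendment E, so it is an assumption here. The planning share is 40% (60% on corticosteroids, Protocol 9.2). The SAP revision history says that Population 2 turned out much smaller than anticipated but gives no number, so p = 10% to 40% is shown.

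**The plan's own figures.** The documents print no alpha1 or alpha2 for the 99% allocation. The only stated figures that depend on a split are the 81% and 54% power values, at a 75% allocation. They cannot be reproduced firmly, because the placebo rate and the share of OS 4 patients behind them are not given. The Amendment D power values do reproduce: 47.3% and 82.7%, against 47% and 83%.

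**Step 1: the three rules.** Under both nulls, with bivariate normal statistics, let

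U(a1, a2) = P(p1 < a1 or p2 < a2) = a1 + a2 − P(p1 < a1 and p2 < a2).

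- Plain split (6.11.1): a1 = 0.99 × 0.025 = 0.02475; a2 = 0.01 × 0.025 = 0.00025.
- Weighted parametric test (6.6): find c with U(c × 0.02475, c × 0.00025) = 0.025. The common factor c is inferred from how a weighted parametric test works; the SAP does not print it.
- Protocol 9.1: keep a1 = 0.02475 and solve U(0.02475, a2) = 0.025 for a2.

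| p | correlation | U, plain split | 6.6: alpha1 | 6.6: alpha2 | 6.6: sum | Protocol alpha2 |
|---|---|---|---|---|---|---|
| 10% | 0.316 | 0.02495 | 0.02480 | 0.000251 | 0.02505 | 0.00031 |
| 20% | 0.447 | 0.02491 | 0.02484 | 0.000251 | 0.02509 | 0.00039 |
| 40% | 0.632 | 0.02483 | 0.02492 | 0.000252 | 0.02517 | 0.00065 |

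The other two rules have U = 0.025 by construction. There are therefore two distinct Population 2 thresholds (about 0.00025, and the protocol's value) and two slightly different Population 1 thresholds.

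**Step 2: how often the verdict differs.** Pairs (z1, z2) were simulated, 4 million per scenario, treating Population 2 as the non-steroid patients. The table gives the chance that any two of the three rules disagree on trial success.

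| Effect, steroid / non-steroid | p = 10% | p = 20% | p = 40% |
|---|---|---|---|
| 0.040 / 0.075 (plan) | 0.07% | 0.17% | 0.43% |
| 0.075 / 0.075 (plan) | 0.01% | 0.03% | 0.05% |
| 0 / 0.075 | 0.13% | 0.58% | 2.5% |

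Reaching 2% to 5% at every share takes no effect at all in steroid users and a larger effect in Population 2 than the plan assumes: 20, 15 and 10 points at shares of 10%, 20% and 40%. The two SAP rules alone disagree in at most about 0.11% of trials.

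**Step 3: the key-secondary branch.** Suppose Population 1 is truly effective and almost surely rejected, while the Population 2 null and one secondary null are true. Under SAP 6.6 the error in that intersection is P(p2 < alpha2 or p_sec < alpha1). It equals 0.025 only if the secondary statistic's correlation with z2 is sqrt(p). If they are uncorrelated it is alpha1 + alpha2 − alpha1 × alpha2:

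- p = 10%: 0.02480 + 0.000251 − 0.000006 = 0.02504 (0.025045 before rounding)
- p = 40%: 0.02492 + 0.000252 − 0.000006 = 0.02517

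The excess over 0.025 is about 0.00005 to 0.00017.

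**The case against.** The strongest reply is that SAP 6.6 is specific and declared final, so 6.11.1 is shorthand for the same 99:1 weights. On Population 2 the two SAP sections do give practically the same threshold. Protocol 9.1 delegates details to the SAP and says that the final levels, in the plural, depend on the share observed. SAP 6.6 openly notes a departure from the protocol. Most of this stands: the intended rule can be identified, and it is 6.6.

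Two things remain. Elsewhere the documents use such a percentage as the level itself: 75% of total alpha for alpha1 in Protocol 9.2, and a 90% allocation labelled alpha1 in SAP 6.16.2. A literal reading of 6.11.1 is therefore reasonable. And the text after the departure note describes the testing sequence and the late retest of Population 2; it never says that the calculation of alpha2 changed.

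A reader might infer that the Population 2 threshold is uncertain by a factor of 2.6 (0.00065 against 0.00025). That needs the 40% planning share, which SAP Version 4 indicates was not met; at an assumed 10% to 20% the ratio is 1.25 to about 1.5. A reader might also infer that the SAP rule is wrong because the protocol's rule has more power. It is a trade: 6.6 gives a slightly higher alpha1 to the population carrying 99% of the weight.

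On the key secondaries, the excess is an upper bound. It shrinks with positive correlation: at a 20% share and an assumed endpoint correlation of 0.7 it is about 0.00004.

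**Conclusion.** The point holds as a minor one. The wording yields two Population 1 thresholds (0.02475, or 0.02480 to 0.02492) and two Population 2 thresholds (about 0.00025, or 0.0003 to 0.0004 under the protocol's rule at an assumed 10% to 20% share).

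The documents do not support reading this as type I error inflation across the two primaries: every rule stays at or below 0.025. Nor do they support a material risk to the trial's verdict, since disagreement is below 0.5% under the plan's effects and reaches a few percent only if benefit is confined to Population 2.

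Separately, the strong-control claim in SAP 6.6 is not met exactly when only Population 1 is rejected. The excess is at most about 0.00005 to 0.00017.

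These sizes rest on N = 1400, a 25% placebo rate, a Population 2 share of 10% to 40%, bivariate normality, and the inferred common scaling in gMCP.

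**What to change.** Before unblinding:

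1. In SAP 6.11.1, replace the sentence on the 99% split with a reference to 6.6: weights 0.99/0.01, both levels computed in gMCP at the observed p. In 6.6, state that this replaces the alpha2 calculation in Protocol 9.1.
2. In SAP 6.6, when Population 1 is rejected and Population 2 is not, do not test the key secondaries at the scaled alpha1. Use either 0.025 − alpha2 (about 0.02475), or 0.99 × 0.025 = 0.02475 with Population 2 held at its unscaled 0.00025 in that intersection. Either is a plain Bonferroni test and needs no correlation between a secondary and Population 2.

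The cost is a few lines of SAP text and no new data. The key-secondary level in that branch falls by about 0.00005 to 0.0002. Adopting the protocol's alpha2 rule instead is optional; it is not needed to correct the plan.

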### **6.16.2. Sample Size Re-Estimation**

This section provides an overview of design parameters for this sample size adaptive trial. It includes a detailed description of the unblinded sample size procedure and associated formulas for executing the design.

For purposes of sample size re-estimation, the overall  $\alpha$  will be split such that 90% is allocated to Population 1 ( $\alpha_1$ ).

The proposed sample size re-estimation may result in overall sample sizes from approximately 1400 patients to 1700 patients.

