#### **6.16.2.1. Execution Details**

An interim analysis will be performed when approximately 1000 patients have randomized in the trial and had the opportunity to contribute data to the primary endpoint (i.e., had the opportunity to complete the study or discontinued). This analysis will be used to determine the final sample size of the trial, in accordance with adaptive SSR methodology described in Mehta and Pocock (2011). Discontinuing the study due to safety concerns at the interim is also possible. Due to the uncertainty in enrollment projections, the exact timing of the interim may occur at a sample size smaller or larger than the planned number of 1000 patients.

At the interim analysis, the conditional power (CP) for statistical significance of the primary endpoint will be calculated for each of the two population separately using the CP formula as given in Mehta and Pocock (2011) for each dose-placebo comparison. The maximum of the two conditional powers will be considered. This CP could fall into one of the three zones: “Unfavorable” ( $CP < 30\%$ ), “Promising” ( $30\% \leq CP < 90\%$ ), and “Favorable” ( $CP \geq 90\%$ ). Sample size will be increased if the maximum of two CPs falls in the promising zone but will remain at the minimum otherwise.

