**Table KHAA.6.13. Defining the Values for the Conditional Power Calculation**

Quantity	Input Value or Derivation/Calculation
$z_1$	This is the chi-square test statistic for testing difference between of baricitinib versus placebo for the primary efficacy analysis conducted using only patients included in the interim analysis .
$n_1$	This is the planned total number of randomized patients included in the interim analysis including both treatment groups. The interim is scheduled to occur when approximately 71% of randomized patients have had the opportunity to complete the treatment phase at $n_1 = 1000$ for Population 1. Due to the uncertainty in enrollment projections, the exact timing of the interim may occur at a sample size smaller or larger than the planned number of 1000 patients for Population 1. For Population 2, $n_1$ will be the number of patients observed at the time of the interim analysis in Population 2
$n_2$	This is the increment from $n_1$ for the total number of patients in both treatment groups should the study remain at the planned minimum sample size based on interim results. The planned minimum sample size is 1400 and if the interim occurs at the planned $n_1 = 1000$ , the increment needed to get to 1400 patients is $n_2 = 400$ for Population 1. For Population 2, the proportion of patients $p$ not on dexamethasone or other systemic corticosteroids will be estimated from the available data for patients requiring supplemental oxygen at baseline. $n_2$ for Population 2 will then be estimated by multiplying $n_2$ for the overall population by the observed proportion, i.e., ( $n_2$ for Population 2) = ( $n_2$ for Population 1) $\times p$

As provided in Mehta and Pocock (2011), the conditional power for the primary efficacy analysis is given by

$$CP(z_1, n_2) = 1 - \Phi\left(\frac{z_\alpha \sqrt{n_1 + n_2} - z_1 \sqrt{n_1}}{\sqrt{n_2}} - \frac{z_1 \sqrt{n_2}}{\sqrt{n_1}}\right)$$

where  $\Phi()$  is the cumulative distribution function of a standard normal variable. The CP will be calculated for Population 1 and for Population 2 with the prespecified split type-I errors  $\alpha_1$  and  $\alpha_2$  respectively. Note that this conditional power calculation assumes that the data post-interim follows a distribution with an effect size equal to the effect size observed at interim. The preceding conditional power formula is written in terms of the test statistic for the baricitinib versus placebo dose comparison.

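### If enrolment stood between 1400 and 1700 when the interim was completed, the SAP lets the interim result choose the final statistic, and one-sided error can rise slightly above 0.025, to about 0.0257

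*SAP*

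**What the plan says.** SAP 6.6 claims: "The testing scheme will provide a strong control of Type-I error for the study at a 1-sided 0.025 level". SAP 6.11.1 carries this through the sample size re-estimation: "The CHW method ensures strong control of type I error when the sample size is increased in a data dependent manner". The same section then makes an exception, judged at the time the interim was completed: "No CHW adjustments will be applied to the endpoints if the recommended increased number of patients from the sample size re-estimation had already been enrolled".

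The design values are in SAP 6.16.2:

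- **Timing (6.16.2.1):** "An interim analysis will be performed when approximately 1000 patients have randomized in the trial".
- **Minimum size (Table KHAA.6.13):** "The planned minimum sample size is 1400", so n1 = 1000 and n2 = 400.
- **Increase rule (6.16.2.1):** the size goes up only if the larger of the two populations' conditional powers is at least 30% and below 90%. Otherwise it stays at the minimum.
- **New size (6.16.2.3):** a formula in z1 that targets 90% conditional power, capped at 1700.
- **CHW weights (6.16.2.4):** √(n1/(n1+n2)) and √(n2/(n1+n2)), which are √(1000/1400) and √(400/1400).

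Population 1 is all randomized patients (6.11.1), and the ITT definition in 6.1.1 agrees. The SAP does not say which patients or which statistic apply when no increase is recommended but more than 1400 patients are already enrolled.

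**The concern.** CHW protects the type I error because its weights are fixed in advance and it is used whatever the interim shows. The exception makes its use depend on whether the recommended size exceeds M. M does not depend on z1, but the recommended size does. For M between 1400 and 1700, a z1 that gives a recommendation above M leads to CHW with 1400-based weights. Any other z1 leads, if all randomized patients are analysed, to the conventional test on M patients. Each statistic has level 0.025 when used for every z1. A choice between them driven by z1 need not.

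At stake is the one-sided 0.025 guarantee for the primary comparisons and, because 6.11.1 extends CHW to them, for the secondary endpoints.

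**Working it through.** **Inputs.** n1 = 1000, minimum 1400, cap 1700, promising zone 30% to 90%, one-sided α = 0.025 (z = 1.96), all from the SAP. M is an assumption and is varied. As a check on the stated timing, 1000/1400 = 71.4%, which agrees with "The interim is scheduled to occur when approximately 71% of randomized patients have had the opportunity to complete the treatment phase".

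**Step 1: the promising zone.** The SAP's conditional power is

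CP = 1 − Φ[(1.96√1400 − z1√1000)/√400 − z1√400/√1000].

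- z1 = 1.42: (73.34 − 44.90)/20 − 0.90 = 0.52, so CP = 30%.
- z1 = 2.235: (73.34 − 70.68)/20 − 1.41 = −1.28, so CP = 90%.

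**Step 2: the recommended size.**

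N_new = 1000 + (1000/z1²)[(1.96√1400 − z1√1000)/√400 + 1.2816]².

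- z1 = 2.0: 1000 + 250 × (0.504 + 1.282)² ≈ 1797, capped at 1700.
- z1 = 2.2: 1000 + 206.6 × (0.188 + 1.282)² ≈ 1446.

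N_new falls as z1 rises and exceeds 1400 throughout the zone. With M = 1500, CHW applies for z1 from 1.42 to 2.16, and the exception applies from 2.16 to 2.235.

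**Step 3: conditional error.** Given z1, the null probability of rejecting with a statistic weighted for total size N is

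A_N(z1) = 1 − Φ[(1.96√N − z1√1000)/√(N − 1000)].

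| z1 | Statistic used when M = 1500 | A_1400 | A_1500 |
|---|---|---|---|
| 2.0 | CHW | 0.307 | 0.286 |
| 2.2 | conventional (exception) | 0.425 | 0.388 |

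**Step 4: the SAP's own level.** Integrating A_1400 over the standard normal density of z1 gives 0.0250. This is the stated level for a fixed 1400, or for CHW with 1000/400 weights used for every outcome.

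**Step 5: the level when z1 chooses.** Using A_M everywhere also gives 0.0250. The level under the switch is therefore 0.025 plus the integral of (A_1400 − A_M) over the z1 values where CHW applies. The table also shows two variants: the exception sentence deleted with nothing else changed, and outcomes without an increase analysed at 1400.

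| M | Excess | Level, all M analysed | Sentence deleted only | No-increase outcomes analysed at 1400 |
|---|---|---|---|---|
| ≤ 1400 | 0 | 0.0250 | 0.0250 | 0.0250 |
| 1450 | 0.00020 | 0.0252 | 0.0252 | 0.0250 |
| 1500 | 0.00036 | 0.0254 | 0.0255 | 0.0249 |
| 1550 | 0.00048 | 0.0255 | 0.0257 | 0.0248 |
| 1600 | 0.00057 | 0.0256 | 0.0259 | 0.0247 |
| 1699 | 0.00069 | 0.0257 | 0.0263 | 0.0244 |

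For M ≥ 1700 every outcome uses the conventional test on M patients under the SAP as it stands, so the level is 0.0250.

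**Step 6: sensitivity.**

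- *Re-estimation alpha.* SAP 6.16.2 has the alpha "split such that 90% is allocated to Population 1" for the re-estimation. Using 0.0225 in Steps 1 and 2 moves the zone to about 1.46 to 2.27. The level becomes 0.0254 at M = 1500 and 0.0258 at M = 1699.
- *Both populations.* A simulation used the larger-conditional-power rule, the 90/10 split at re-estimation and the final split ("99% of alpha is assigned to Population 1 and the rest to Population 2"). It ran 50 million trials for each assumed Population 2 share (10%, 20%, 40%), with standard error about 0.00002. CHW throughout gave a family-wise level of 0.0250. The switch gave 0.0254 (M = 1500), 0.0255 (M = 1550) and 0.0257 (M = 1690), almost the same for every share.
- *Interim size.* Over n1 from 700 to 1350 the largest level found was 0.0260.

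**The case against.** A reader might infer that the primary test simply exceeds 0.025. The documents do not support that. Two conditions are needed, and neither is stated. First, M must lie between 1400 and 1700. Second, outcomes without an increase must be analysed conventionally on all M patients. SAP 6.16.2.1 says that the size then stays at the minimum, and a literal analysis at 1400 would give no excess. This stands as a limit on the claim. The second condition is nevertheless the more natural reading, because Population 1 and the ITT set are all randomized patients and no cut-back to 1400 is described.

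A reader might also infer that the exception sentence is the defect and should be struck out. It is not the sole cause. In the z1 range where it applies, the conventional test is the more conservative of the two (0.388 against 0.425 at z1 = 2.2, M = 1500). Removing the sentence alone raises the error, as the table shows. The excess arises where CHW is used with 1400-based weights while the other outcomes are tested conventionally on M patients.

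Three further points stand. The excess is small. The futility rule is in the DMC charter, which is not available here, and if binding it would lower these figures. Finally, SAP 5.2 places the interim in January 2021, so re-anchoring the weights now could itself look data-dependent if whoever adopts it knew the recommendation.

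**Conclusion.** The concern holds in conditional form. The SAP does not fix one final statistic for every interim outcome. If 1400 < M < 1700 and all randomized patients are analysed, a nominal one-sided 0.025 test has true level 0.0252 (M = 1450) to 0.0257 (M = 1699), an excess of about 1% to 3% of alpha. If M ≤ 1400 or M ≥ 1700 the level is exactly 0.025. If outcomes without an increase are cut back to 1400 it is not above 0.025. The range rests on n1 = 1000, α = 0.025 in both the re-estimation and the final test, and no binding futility rule. The documents do not show which case occurred, so they do not establish that error control was actually lost. They do show that the strong control claimed in SAP 6.6 and 6.11.1 is not guaranteed by the rules as written.

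**What to change.** Replace the exception sentence in SAP 6.11.1, and align 6.16.2.4, with a rule of this kind: if M > 1400 patients were randomized before the interim was completed, n2 = M − n1 in the CHW statistic for every outcome of the re-estimation. Use the corresponding counts for Population 2 and for each key secondary endpoint.

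M does not depend on z1, so these weights are legitimate, and the level is 0.0250 for any M. When no patients are added beyond M, the statistic is the stage-wise form of the conventional test on M patients. When N_new exceeds M, it is CHW with weights √(n1/M) and √((M − n1)/M).

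The rule must be adopted from the enrolment count alone, without knowledge of unblinded interim results, and the SAP should record that. The cost is a short SAP edit before database lock, with no new patients or data. The one downside is that an SAP change made after the interim has to be justified as independent of the interim result.
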